5.2 Derived Variables

The below table provide the list of derived variables for Demographic duration derivation, baseline derivations and other important derivations applicable for this study.

Table 1 Formula for Derived Variables

Variables	Formula
Demographic and Baseline characteristics	
Age at signing of ICF (in years)	integer ((date of screening visit – date of birth + 1)/ 365.25)
Body mass index (BMI) (kg/m ²)	weight (kg)/[height (m)] ²
Derivation of Duration	
Study day at any visit	Date of interest – date of first dose of vaccination. One day is added if this difference is ≥ 0
Baseline Derivations	
Baseline	The baseline value is defined as the last non-missing observation prior to or on the date of the first vaccination dose on Day 1.
Change from baseline	Post baseline value – Baseline
Relative change from baseline	$[(\text{Post baseline value} - \text{Baseline})/\text{Baseline}] * 100$

5.3 Analysis Visit Windows

Analysis visit windows will be used for all visit-based assessments to map longitudinal observations to scheduled visits and thereby allow for by-visit analyses, since not all assessments are performed on the scheduled day. Unless otherwise specified, all longitudinal safety data analyses will be based on the analysis visit windows. The analysis visit windows will be calculated by bisecting the interval between adjacent scheduled visit days except for the first post-treatment visit, the phone call visits, and 2nd vaccination dose visit. These windows are provided for in Table 2:

Table 2 Visit Windows for Analysis

Nominal Visit	Lower Bound	Target	Upper Bound
V2 – Dose 1	1	1	1
Phone Call 1	2	3	4
V3	5	7	Day 28 Dosing Date - 1
V4 – Dose 2	Day 28 Dosing Date	28	Day 28 Dosing Date
Phone Call 2	Day 28 Dosing Date + 1	31	32
V5	33	35	46
V6	47	56	84
V7	85	112	168
V8	169	224	280
V9	281	336	

The actual assessment day will be mapped to the windows defined for each scheduled study visit with following rules:

- If more than one assessment falls within a visit window, the closest non-missing assessment to the scheduled day will be used in the analysis.
- If 2 non-missing assessment actual dates are equidistant from the target day, the later visit will be used in the analysis.
- For retest values of laboratory data, the retest value (the last valid observation assessed on the same visit day) will be chosen.

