6.1.12 Sampling Schedule

See [Table 1](#), and [Table 2](#)[Section 4](#) for the schedules of events.

Blood samples for human immunodeficiency virus (HIV), hepatitis B and hepatitis C: approximately 10 mL is taken at the screening visit. A positive test is exclusionary.

Nasal/nasopharyngeal swab for SARS-CoV-2 virus by PCR or rapid antigen test and viral sequencing:

Nasopharyngeal swabs are taken at the screening visit and all subsequent visits. In Phase 1b, two swabs will be taken, one for SARS-CoV-2 virus testing and one to be stored frozen for potential sequencing at a later time point. A positive test at screening is exclusionary. Timepoints are as follows:

- o Phase 1a: Days 1, 7, 28, 35, 56, 112, 224 and 336
- o Phase 1b: Days 1, 7, 14, 28, 56, 84, 168 and 336

Blood samples for hematology/ biochemistry: approximately 6 mL of blood will be taken at the screening visit and all subsequent visits. Timepoints are as follows:

- o Phase 1a: Days 1, 7, 28, 35, 56, 112, 224 and 336
- o Phase 1b: Days 1, 7, 28, 56, 84, 168 and 336

Blood samples for humoral immune responses: approximately 10 mL of blood will be taken at day 1 and all subsequent visits. Timepoints are as follows:

- o Phase 1a: Days 1, 7, 28, 35, 56, 112, 224 and 336
- o Phase 1b: Days 1, 7, 14, 28, 56, 84, 168 and 336

Blood samples for cell-mediated immune responses: approximately 40 mL of blood will be taken at day 1 and all subsequent visits. Timepoints are as follows:

- o Phase 1a: Days 1, 7, 28, 35, 56, 112, 224 and 336
- o Phase 1b: Days 1, 7, 14, 28 and 336

Urine samples for urinalysis: screening and all subsequent visits. Timepoints are as follows:

- o Phase 1a: Screening and Days 1, 7, 28, 35, 56, 112, 224 and 336
- o Phase 1b: Screening and Days 1, 7, 14, 28, 56, 84, 168 and 336

Urine samples for pregnancy test: screening and day of vaccination. Timepoints are as follows:

- o Phase 1a: Screening and Days 1 and 28
- o Phase 1b: Screening and Day 1

The total amount of blood to be drawn for clinical laboratory tests and immunology evaluations is approximately 15-20 mL for screening and subsequent blood draws that do not include blood samples for cell-mediated immune responses and approximately 55-60 mL for subsequent blood draws that do include blood samples for cell-mediated immune responses.

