6.3.2 Clinical Laboratory Evaluation

6.3.2.1 Overall

An overall summary of laboratory abnormalities (hematology, biochemistry, and urinalysis) will be created for events taking place at Day 56 and 28 days after each study vaccination. This summary will present the counts and percentages of subjects experiencing each type and will further break down abnormalities by severity.

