6.3.2.2 Hematology

A summary of hematology lab results for the absolute and change from baseline values will be presented by visit.

A listing for hematology results will be created together with the normal ranges and severity grades. Lab values that are below or above the normal ranges will be flagged.

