6.4.1 Immunogenicity Evaluations

Immunogenicity will be assessed by measuring serum nAB titers against wild-type SARS-CoV-2 virus (PRNT) and/or spike protein-expressing pseudovirus (microneutralization), serum binding antibody titers against spike protein and the spike protein receptor-binding domain (RBD), and peripheral blood mononuclear cell (PBMC) T cell responses against spike protein.

Testing will include assessment of responses against spike protein of the original SARS-CoV-2 isolate as well as spike protein of variant Beta (B.1.315) and other variants. In Phase 1a, time points for evaluation will be at Study Days 1, 7, 28, 35, 56, 112, 224 and 336. In Phase 1b, time points for evaluation for groups G4 and G5 will be at Study Days 1, 7, 14, 28, 56, 84, 168 and 336.

Neutralizing antibody and binding antibody results will be presented as the geometric mean titer (GMT) and the geometric mean fold increase in titer post-vaccination over baseline. T cell responses will be presented as the geometric mean number of IFN-ELISPOT-positive cells per 10^6 PBMCs.

Geometric mean nAb titers and antibodies to the receptor binding domain (RBD) for 5 µg and 10 µg dose groups at Day 1, 7, 28, 35 and 56 will be compared to each other and pooled COVID-19 convalescent serum to select the optimal dose of VBI-2902a in the age cohorts.

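### The SAP's only analysis-window table follows the Phase 1a two-dose schedule, so by-visit laboratory summaries for Phase 1b are mislabelled, dropped or left without a window

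*SAP*

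**What the plan says.** SAP 5.3 opens with a general scope: "Analysis visit windows will be used for all visit-based assessments to map longitudinal observations to scheduled visits". It then makes the windows the default for safety, so that unless otherwise specified "all longitudinal safety data analyses will be based on the analysis visit windows". It describes the construction as bisection between neighbouring scheduled days, with exceptions for the first post-treatment visit, the phone calls and the second-dose visit, and then says "These windows are provided for in Table 2". When two results share a window, "If more than one assessment falls within a visit window, the closest non-missing assessment to the scheduled day will be used in the analysis".

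Table 2 carries no phase label. Its rows include a second-dose visit (V4), a second phone call, and visit targets on Days 7, 28, 35, 56, 112, 224 and 336. The V3 upper bound, both V4 bounds and the lower bound of the second phone call are expressed through the Day 28 dosing date.

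For Phase 1b, SAP 6.4.1 says "time points for evaluation for groups G4 and G5 will be at Study Days 1, 7, 14, 28, 56, 84, 168 and 336". The hematology and biochemistry list in Protocol 6.1.12 reads "Phase 1b: Days 1, 7, 28, 56, 84, 168 and 336", and urinalysis is also collected on Day 14. SAP 6.3.2.2 says "A summary of hematology lab results for the absolute and change from baseline values will be presented by visit", and chemistry and quantitative urinalysis follow the same pattern. There is no second window table.

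**The concern.** Table 2 is the stated source of the windows for both phases, but it describes only one of them. G4 and G5 have no second dose, no Day 35, 112 or 224 visit, and do have Day 14, 84 and 168 visits that Table 2 does not target. A program written to the SAP would put some Phase 1b results under the wrong day, discard others as the more distant of two values in a window, and fail to place those whose window depends on a dose never given.

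The direct effect is on the by-visit laboratory tables. The antibody effect is conditional. GMT and fold-rise on Days 14, 28, 84 and 168 are at stake if the opening sentence of 5.3 covers immunogenicity, and Protocol 4.10 singles out Day 168 alongside Day 56 for Phase 1b. SAP 6.4 does not say whether windows or nominal visits apply.

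**Working it through.** **Inputs.** Table 2 windows and the closest-value rule come from SAP 5.3. Phase 1b visit days and permitted intervals come from the schedules of events (Protocol Table 2, SAP Table 4): Day 7 (+3), 14 (+3), 28 (±3), 56 (±3), 84 (±7), 168 (±14), 336 (±14).

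**Step 1: reproduce Table 2.** Midpoints of the Phase 1a days are (35+56)/2 = 45.5, rounded up to 46; (56+112)/2 = 84; (112+224)/2 = 168; (224+336)/2 = 280. These are exactly the tabulated upper bounds for V5 to V8. The Phase 1b midpoints are 10.5, 21, 42, 70, 126 and 252, and none of them matches.

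**Step 2: map each permitted Phase 1b day through Table 2.**

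| Phase 1b visit | Permitted days | As written (no dose-2 date) | If Day 28 stands in for the dosing date |
|---|---|---|---|
| Day 7 | 7–10 | Upper bound undefined | Day 7 window |
| Day 14 | 14–17 | No target; upper bound undefined | Day 7 window |
| Day 28 | 25–31 | No defined window | 25–27: Day 7 window; 28: dose-2 visit; 29–31: Phone Call 2 |
| Day 56 | 53–59 | Day 56 window | Same |
| Day 84 | 77–91 | 77–84 (8 days): Day 56 window; 85–91 (7 days): Day 112 window | Same |
| Day 168 | 154–182 | 154–168 (15 days): Day 112 window; 169–182 (14 days): Day 224 window | Same |
| Day 336 | 322–350 | Day 336 window | Same |

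The Day 84 and Day 168 rows need no assumption about a second dose.

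**Step 3: apply the closest-value rule.**
- A Day 84 result taken on days 77–84 is 77−56 = 21 to 84−56 = 28 days from the Day 56 target. A Day 56 result within its interval is at most 3 days away. The Day 84 result is dropped, or reported as Day 56 if the Day 56 value is missing.
- With Day 28 substituted, a Day 14 result is 7 to 10 days from the Day 7 target, against 0 to 3 for the Day 7 result. It is dropped whenever a Day 7 value exists.
- A late Day 84 (85–91) and an on-time or early Day 168 (154–168) share the Day 112 window. Their distances from 112 are 21–27 and 42–56 days, so the Day 168 result is always dropped. This covers 7 × 15 = 105 of the 15 × 29 = 435 permitted date pairs.

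**Step 4: count affected days.** Hematology and biochemistry have 6 post-dose Phase 1b days, of which 28, 84 and 168 are affected (3 of 6). Urinalysis, and antibodies if windowed, have 7, of which 14, 28, 84 and 168 are affected (4 of 7). Day 7 is counted as correct although its upper bound is open. If Day 28 is substituted, a participant seen exactly on Day 28 does land on a Day 28 target, labelled as the second dose. The counts for someone exactly on schedule are then 2 of 6 and 3 of 7. The other 6 of the 7 permitted Day 28 days still miss.

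**The case against.** The strongest reply is that 5.3 states a general bisection rule and the SAP contains the Phase 1b schedule. A programmer who saw a second-dose row applied to a one-dose group would derive the right windows or ask. That is plausible, and it means the misassignment is what the text produces rather than a certainty about the final outputs. But the SAP says the windows are those in Table 2, and the rule exempts the first post-treatment visit, so the Day 7 upper bound cannot be derived from it.

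A second reply is that Table 2 labels are visit numbers, so V7 means Day 84 and V8 means Day 168 in Phase 1b. That rescues only late visits (85–91 and 169–182). On schedule, Day 84 still falls in V6, which is Day 56, and Day 168 in V7, which would be Day 84.

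A third is that the consequence is modest. This largely stands. The by-visit tables are descriptive, listings keep every value, and adverse-event rates counted from vaccination do not use the windows. The laboratory-abnormality summary for "events taking place at Day 56 and 28 days after each study vaccination" can be built from dates, and is affected only if its records are selected by analysis visit. The fold-rise model in 6.4.2 uses Day 56, which maps correctly; it is touched only if a Day 77–84 sample replaces a missing Day 56 value. Finally, 105 of 435 counts permitted date pairs and is not an expected frequency.

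**Conclusion.** The concern holds and should be fixed. As written, the SAP gives no usable Phase 1b windows for Days 14, 28, 84 and 168, and Table 2 misplaces exactly on-schedule Day 84 and Day 168 results under any reading of the missing dose-2 date. Days 56 and 336 map correctly, as does Day 7 once an upper bound is supplied.

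The effect on by-visit laboratory summaries follows from the text of 5.3. The effect on antibody summaries depends on whether 5.3 governs immunogenicity, which is unstated. The 3-of-6 figure takes the day list in Protocol 6.1.12, which omits Day 14, as governing hematology and biochemistry. Nothing here alters data collection or the listings.

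**What to change.** Title Table 2 as Phase 1a and add a Phase 1b table. Bisection with Table 2's rounding (half-days up) gives:

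| Visit | Window (study days) |
|---|---|
| Day 7 | 5–11 |
| Day 14 | 12–21 |
| Day 28 | 22–42 |
| Day 56 | 43–70 |
| Day 84 | 71–126 |
| Day 168 | 127–252 |
| Day 336 | 253 onward |

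Day 1 and the first phone call can keep their Table 2 rows. All 4 + 4 + 7 + 7 + 15 + 29 + 29 = 95 permitted Phase 1b visit days then fall in their own window. The Day 7 upper bound is a choice: 10 serves equally well, since no permitted visit falls on Day 11. The sponsor should also say whether hematology and biochemistry, with no Day 14 draw, use a different Day 7/Day 28 boundary. Stating that Phase 1b uses nominal visits is an acceptable alternative.

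Add one sentence to 6.4 saying whether windows or nominal visits apply to immunogenicity samples.

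A minor related correction for Phase 1a is to define the second phone call and V5 windows from the actual second-dose date. At present a permitted V5 visit on Day 32 (1 of the 7 days 32–38) is labelled as the phone call.

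The cost is one SAP table, one sentence and a programming change, with no effect on trial conduct.

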4 STUDY DESIGN

4.1 Design

Overview

The trial is a phase 1a/1b study is a randomized, observer-blind, placebo-controlled.

Description of study parts and groups

A schematic of the study design is shown in Figure 1.

Phase 1a

60 healthy adults, age 18-54 years of age with no previous clinical or laboratory diagnosis of COVID-19 or SARS-CoV-2 infection and not previously received an experimental or authorized COVID-19 vaccine will be enrolled into the Phase 1a part of the study to evaluate the safety, tolerability and immunogenicity of a one-dose or two-dose regimen of VBI-2902a at a dose level of 5 µg of S protein or placebo. Participants will be randomized at a 2:1 ratio to VBI-2902a or placebo:

- **Group G1** – 20 participants will receive VBI-2902a at a dose of 5 µg of S protein at Day 1 and placebo at Day 28.
- **Group G2** – 20 participants will receive VBI-2902a at a dose of 5 µg of S protein at Days 1 and 28.
- **Group G3** – 20 participants will receive placebo at Days 1 and 28.

An Independent Data Safety Monitoring Board (DSMB) will review blinded safety data (reactogenicity, adverse events (AEs) and safety laboratory assessments) at Day 7 after the first vaccination. The second vaccination will only be given if the DSMB confirms that Day 7 safety is acceptable and that stopping rules were not met. The DSMB will further review blinded post-vaccination safety through Day 35, 7 days after the second vaccination and through Day 56, 28 days after the second vaccination. A Study Steering Committee (SSC), comprised of representatives from the study sponsor (not involved in study operations) and external vaccine experts, will review unblinded immunogenicity data 7 days and 28 days after the second vaccination. The study will be unblinded following DSMB review of safety data collected through Day 56.

Phase 1b

A total of 54 healthy adults, age 18-54 years, with no history of clinical or laboratory diagnosis of SARS-CoV-2 infection or COVID-19 illness, will be enrolled in the Phase 1b part of the study.

Participants who had been previously vaccinated with authorized mRNA COVID-19 vaccine(s) will be randomized at a 1:1 ratio to receive, in a blinded fashion, one dose of VBI-2905a or placebo:

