On the vaccination visits, participants will remain at the site for at least 60 minutes for an evaluation of AEs and vital signs. Participants will be contacted by phone 3 days after each vaccination for a safety follow up call. Diary cards will be distributed to study participants at vaccination visits to record body temperature, local and systemic reactions from day of the vaccination(s) and the next 6 days. Serious AEs (SAEs) and medically-attended AEs (MAAEs) will be recorded throughout the study.

In Phase 1a, participants will visit the study site for dose administration, safety assessments and blood sample collection on Days 1 and 28 (prior to study vaccination) and for safety assessments and blood sample collection on Days 7, 35, 56, 112, 224 and 336.

In Phase 1b, participants will visit the study site for dose administration, safety assessments and blood sample collection on Day 1 for safety assessments and blood sample collection on Days 7, 14, 28, 56, 84, 168 and 336. Study participants will be tested for SARS-CoV-2 infection by PCR or rapid antigen test and surveilled for signs and symptoms of COVID-19 illness throughout the study. Duplicate nasopharyngeal swab samples will be retained for storage and potential sequencing of viral RNA should samples test positive for SARS-CoV-2 infection.

Participants will be followed until the study completion on Day 336. If a subject is lost to follow-up, every effort will be made by the study center personnel to contact the subject and to determine the reason for discontinuation. Measures taken to follow-up will be documented.

Figure 1: Clinical Trial Design

* Not previously vaccinated with any licensed or experimental COVID-19 vaccine and no history of clinical or laboratory diagnosis of SARS-CoV-2 infection or COVID-19 illness

** Received a full course of an authorized mRNA COVID-19 vaccine at least 4 months prior to the study and no history of clinical or laboratory diagnosis of SARS-CoV-2 infection or COVID-19 illness

Table 1: Phase 1a Schedule of Events

Schedule of Events	Screening								Study Period	End-of Study Early D/C	
	1	2	Phone Call	3	4	Phone Call	5	6	7	8	9
Visit											
Study Day	-28 to -1	1	3	7	28	31	35	56	112	224	336
Study Month (28 days)	<-1	0	0.1	0.25	1	1.1	1.25	2	4	8	12
Visit Intervals (Days)	n/a	n/a	±1	+3	±3	±1	±3	±3	±7	±14	±14
Informed consent	●	●									
Inclusion/exclusion criteria	●										
Confirm ongoing eligibility		●									
Demographics	●	●	●								

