6.1.13 Study Product Administration

After completing all prerequisite procedures prior to injection, one dose of study vaccine/placebo will be administered IM in the deltoid of either the right or left arm. The second injection in two-dose groups will be administered IM in the deltoid of the opposite arm. Reasons for participant refusal for site rotation will be documented in the eCRF. If the investigator or qualified designee determines that the participant's health on the day of administration temporarily precludes administration, the visit will be rescheduled within the allowed interval for this visit (N/A for Day 1; +/- 3 days for Day 28).

Participants will be observed for 60 minutes following the administration of their injection.

Appropriate medical treatment will be readily available in case of anaphylaxis.

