6.1.15 Recording of AEs, SAEs, and Potential Immune-Mediated Diseases

The participants will be instructed to contact the investigator/study personnel immediately should they manifest any signs or symptoms they perceive as serious (see [Section 8](#)).

At the vaccination visit, 7-day diary cards will be provided to the participant. The participant will record body temperature (oral) and any local/systemic adverse events (AEs)

(i.e., on the day of injection and during the next 6 days). The study center will contact the participant at 3 days (+/- 1 day) post-vaccination to assess participant status and to remind the participant to complete the diary cards. The participant will be instructed to return the completed diary card to the investigator/study personnel at the next study visit.

Any unreturned diary cards will be sought from the participant through telephone call(s) or any other convenient procedure. The investigator/study personnel will transcribe the collected information into the eCRF in English.

Diary cards are considered source documents.

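### SAP Table 2 windows the Phase 1a Day 35 and Day 56 visits from dose 1 instead of from dose 2, and always files a permitted Day 32 visit as a phone call

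*SAP*

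**What the plan says.** Protocol 4.1 has the DSMB review blinded Phase 1a safety data "through Day 35, 7 days after the second vaccination and through Day 56, 28 days after the second vaccination", and SAP 3 repeats this timing. The steering committee reviews unblinded immunogenicity at the same two points. Protocol 4.4 makes the neutralizing titers at Day 28 and Day 56 the primary determinant for immunogenicity.

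The second injection has its own tolerance in Protocol 6.1.13: "N/A for Day 1; +/- 3 days for Day 28". All three Phase 1a groups receive a second injection, active or placebo. The Table 1 row of permitted intervals reads "Visit Intervals (Days) n/a n/a ±1 +3 ±3 ±1 ±3 ±3 ±7 ±14 ±14", which gives Visit 5 as Day 35 ±3 and Visit 6 as Day 56 ±3.

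SAP 5.2 derives study day as "Date of interest – date of first dose of vaccination", with one day added when the difference is not negative. SAP 5.3 bisects the intervals between scheduled days, "except for the first post-treatment visit, the phone call visits, and 2nd vaccination dose visit". V5 and V6 are not among the exceptions. In SAP Table 2 the dose 2 date enters only the V3 upper bound, V4 and the Phone Call 2 lower bound. V5 is fixed at Days 33 to 46 and V6 at Days 47 to 84.

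**The concern.** Two visits that the documents define by dose 2 are placed by a clock that starts at dose 1, although dose 2 itself may move by three days either way. Table 2 uses the actual dose 2 date for the rows just before V5 and then drops it for V5 and V6, where it matters most.

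Three things are at stake. First, results labelled 7 and 28 days after dose 2 mix quite different intervals, in groups of only 20. Second, Table 1 permits Visit 5 from Day 32 while Table 2 starts V5 on Day 33, so a visit that complies with the protocol is filed under a phone call. SAP 5.4 imputes no missing data, so V5 is then blank for that participant unless another assessment falls in Days 33 to 46. Third, participants who miss dose 2 have no dosing date from which to build the windows that need one. This group is foreseeable: Protocol 4.2 stops further vaccination after a positive test, and Protocol 9.2 keeps such participants in follow-up for safety and immunogenicity.

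**Working it through.** **Inputs.** Dose 2: Day 28 ±3 = Days 25 to 31 (Protocol 6.1.13 and 7.11). Visit 5: Day 35 ±3 = Days 32 to 38. Visit 6: Day 56 ±3 = Days 53 to 59 (Protocol Table 1). Call: 3 ±1 days after vaccination (Protocol 6.1.15). SAP Table 2: Phone Call 2 = dose 2 date + 1 to Day 32; V5 = Days 33 to 46; V6 = Days 47 to 84.

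**Step 1: reproduce Table 2.** Midpoints: (35 + 56)/2 = 45.5, rounded up to 46; (56 + 112)/2 = 84; (112 + 224)/2 = 168; (224 + 336)/2 = 280. All four match the stated upper bounds. The V5 lower bound of 33 is the Phone Call 2 upper bound (31 + 1 = 32) plus 1. The nominal gaps 35 − 28 = 7 and 56 − 28 = 28 match the text.

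**Step 2: days from dose 2 to visit.** Minimum = first visit day − 31. Maximum = last visit day − 25.

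| Visit | Visit days | Minimum | Maximum |
|---|---|---|---|
| Visit 5, protocol interval | 32–38 | 32 − 31 = 1 | 38 − 25 = 13 |
| Visit 5, in interval and analysed as V5 | 33–38 | 33 − 31 = 2 | 38 − 25 = 13 |
| Anything mapped to V5 | 33–46 | 33 − 31 = 2 | 46 − 25 = 21 |
| Visit 6, protocol interval | 53–59 | 53 − 31 = 22 | 59 − 25 = 34 |
| Anything mapped to V6 | 47–84 | 47 − 31 = 16 | 84 − 25 = 59 |

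**Step 3: Day 32.** The Phone Call 2 lower bound runs from 25 + 1 = 26 to 31 + 1 = 32, and its upper bound is always 32. Day 32 is therefore in the Phone Call 2 window for every permitted dose 2 day. With dose 2 on Day 25, a visit exactly 7 days later is 25 + 7 = Day 32 and is filed as the call.

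**Step 4: the reverse case.** With dose 2 on Day 31, a call 2 to 4 days later falls on Days 33 to 35, inside the V5 window. A call yields no blood sample, so the harm here is small.

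**Step 5: direction.** Of the 7 × 7 = 49 permitted pairs of dose 2 day and Visit 5 day, 21 give under 7 days, 7 give exactly 7 and 21 give more. Among the 7 × 6 = 42 pairs that Table 2 maps to V5 (Days 33 to 38), 15 are under 7, 6 equal 7 and 21 are over. These are counts of permitted combinations and do not forecast attendance.

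**Step 6: no dose 2.** The V3 upper bound, both V4 bounds and the Phone Call 2 lower bound refer to a date that does not exist. V5 to V9 have fixed bounds and remain defined.

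**The case against.** The best defence is that most of the harm one might fear does not follow, and much of that defence stands.

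- *Bias.* A reader might infer that early Day 35 samples pull the two-dose against one-dose contrast toward no difference. Step 5 does not support that: the permitted spread is symmetric around 7 days, and the part analysed as V5 leans late.
- *A 1-day gap analysed as Day 35.* This needs a Day 32 visit after a Day 31 dose, and Table 2 does not analyse that visit as V5. The shortest gap analysed is 2 days.
- *Truncated reactogenicity.* The solicited-event endpoint is defined as 7 days after each vaccination, not by visit window. Protocol 6.1.15 has the participant "return the completed diary card to the investigator/study personnel at the next study visit" and has unreturned cards chased. DSMB outputs follow a separate SAP that is not among the documents.
- *A call before the dose.* Table 1 read alone would allow it, but Protocol 6.1.15 ties the call to vaccination. This is a discrepancy to reconcile, not an expected event.
- *Lost serum results.* The first sentence of SAP 5.3 covers all visit-based assessments, but a later one specifies only longitudinal safety data, and SAP 6.4 names nominal days without windows. Misfiling of serum is a fair reading, not a certainty.
- *Timing.* Protocol 4.8 starts Phase 1b enrolment after the Phase 1a Day 56 review, and the SAP is dated October 2022. Phase 1a visits have very probably taken place, so a new visit schedule would come too late.

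None of this removes the wrong anchor, the Day 32 mapping or the undefined windows. All three are stated rules of the SAP and can still be corrected there.

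**Conclusion.** The point holds as a defect of SAP Table 2. V5 and V6 are anchored to dose 1 although they are defined by dose 2. In-interval visits analysed as V5 lie 2 to 13 days after dose 2 where 7 is intended, and in-interval V6 visits lie 22 to 34 days after it where 28 is intended. For anything mapped to these visits the ranges are 2 to 21 and 16 to 59 days. A compliant Day 32 visit is always misfiled. The rows that depend on the dose 2 date are undefined without dose 2, but it would go too far to say that such participants have no valid laboratory windows at all.

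The main assumption is that the ±3 intervals in Table 1 are read around the nominal study day, as the table is laid out. If sites schedule Visit 5 at dose 2 + 7 ±3 instead, the mapping gets worse after an early dose: with dose 2 on Day 25, 4 of the 7 possible days (Days 29 to 32) fall in the Phone Call 2 window. How many participants are affected cannot be told from the documents. The correction is worth making because it is cheap and the rule is wrong as written.

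**What to change.** In SAP Table 2:

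- Define Phone Call 2, V5 and V6 by days since the actual dose 2 date. Subtracting 28 from the present bounds gives, for example, V5 = dose 2 + 5 to + 18 (target + 7) and V6 = dose 2 + 19 to + 56 (target + 28). The V7 lower bound then follows at dose 2 + 57.
- Map site-visit assessments only to site-visit windows. With a V5 lower bound of + 5, a permitted Visit 5 held 1 to 4 days after dose 2 (10 of the 49 pairs) would have no window. The SAP should say whether such visits are only listed or are brought in by starting V5 for site visits at dose 2 + 1.
- For participants without dose 2, use nominal Day 28 as the anchor. Give V4 a width, such as the protocol's own Days 25 to 31, and end V3 the day before.
- State that the windows also apply to immunogenicity data.
- Report days since dose 2 at V5 and V6 by group.

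Separately, the Table 1 intervals in the protocol must be reconciled with the 7-days-after-dose-2 description in Protocol 4.1 and the call timing in Protocol 6.1.15. Which schedule is right is for the sponsor to say.

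The cost is minor reprogramming, using dates already recorded.
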